### **5.9 Subject Replacement Strategy**

Patients who drop out before starting pembrolizumab will be replaced. In addition, patients who come off study before completing surgery without grade  $\geq 3$  toxicity will be replaced. The frequency of each of these events will be reported and reasons for replacement reviewed.

### **5.10 Clinical Criteria for Early Trial Termination**

Early trial termination will be the result of the criteria specified below:

1. Quality or quantity of data recording is inaccurate or incomplete
2. Poor adherence to protocol and regulatory requirements
3. Incidence or severity of adverse drug reaction in this or other studies indicates a potential health hazard to subjects
4. Plans to modify or discontinue the development of the study drug

In the event of Merck decision to no longer supply study drug, ample notification will be provided

so that appropriate adjustments to subject treatment can be made.

## 6.0 TRIAL FLOW CHART

### 6.1 Study Flow Chart

Trial Period:	Screeninga		Treatment Cyclesb			Surgical Treatment	Follow-Up
Treatment Cycle:	Screening	1	2	End- Induction/ Safety Visit	SRTc	Surgical Treatment	Post-Treatment/ Safety Visitse
Scheduling Window:	-28d to -1d	± 3d	± 3d	No later than 7d (± 3d)	No later than 7d (± 3d)	no later than 6wksd	At 30d, 90d, 180d,360d after surgery (+14d)
Administrative Procedures							
Informed Consent	X						
Inclusion/Exclusion Criteria	X						
Demographics and Medical History	X						
Prior and Concomitant Medication Review	X	X	X	X		X	X
Trial Treatment Administration		X	X				
Post-study anticancer therapy status							X
Survival Status							X
Clinical Procedures/Assessments							
Review Adverse Events		X	X	X		X	X
Full Physical Examination	X						
Directed Physical Examination		X		X			X
Vital Signs and Weight	X	X		X			X
ECOG Performance Status	X	X		X			X
Laboratory Procedures/Assessmentsf							
Pregnancy Test – Urine or Serum β-HCGg	X						
Coagulation	X						

UCSF Helen Diller Family Comprehensive Cancer Center

Version date: 03/29/2021

Protocol CC#: 166520

Trial Period:	Screening a		Treatment Cycles b			Surgical Treatment	Follow-Up
Treatment Cycle:	Screening	1	2	End- Induction/ Safety Visit	SRT c	Surgical Treatment	Post-Treatment/ Safety Visit e
Scheduling Window:	-28d to -1d	± 3d	± 3d	No later than 7d (± 3d)	No later than 7d (± 3d)	no later than 6wksd	At 30d, 90d, 180d,360d after surgery (+14d)
Hematology	X	X	X	X		X	X
Comprehensive Serum Chemistry Panel	X	X	X	X		X	X
Urinalysis	X						X
Thyroid function	X			X			X
Efficacy Measurements h							
Tumor Imaging (F-18 FDG PET/CT in screening with MRI/CT brain in stage II/III patients, and CT chest at 360d or as otherwise clinically indicated)	X						X
Tumor Biopsies/Archival Tissue Collection/Correlative Studies Blood i							
Archival or Newly Obtained Tissue Collection	X						X
Correlative Studies Blood Collection	X		X	X		X	X

aScreening procedures to be completed within 28 days of C1D1 with the exception of fresh tumor specimens and tumor imaging, please see information in footnotes, respectively.

bPatients receive 2 cycles of pembrolizumab. 1 cycle is defined as 3 week intervals.

cIf patient is scheduled to receive SRT, the day of radiation therapy will be no later than 7d (+/- 3d) following the second cycle of pembrolizumab.

dNo later than 6 weeks after the last dose of pembrolizumab.

eAfter surgery, patients to return for clinical and laboratory assessments at 30 days (first follow-up visit to occur), 90 days, 180 days, and 360 days (+ 21 days) after date of surgery.

fScreening labs performed within 10d of treatment initiation can be applied to Cycle 1 lab tests. After Cycle 1, pre-dose laboratory procedures can be conducted up to 72 hours prior to dosing. Results must be reviewed by the investigator or qualified designee and found to be acceptable prior to each dose of trial treatment.

gFemales of childbearing potential: negative urine or serum pregnancy test within 3d prior to receiving trial treatment. If urine test is positive or non-confirmatory, a serum pregnancy test will be required.

hAll patients to have a full-body F-18 FDG PET/CT scan ≤75d prior to study treatment; patients with stage II and stage III disease should also have brain CT or MRI ≤75d prior to study treatment. Additional imaging during treatment will be under investigator discretion. During Follow-up phase, imaging studies are to be completed at the discretion of investigator or qualified designee.

iNewly obtained specimen is preferred, however archived tissue will be acceptable due to inaccessibility or subject safety concern. Specimens that are newly obtained are defined as collection up to 120d prior to initiation of study treatment.

**For correlative studies and blood collection:** research-donated blood will be collected pre-pembrolizumab infusion for cycle 1 and cycle 2, at the safety visit during cycle 2 (blood should be collected prior to SRT administration if patient will receive SRT), prior to surgical treatment, and at each post-treatment/safety follow-up visit (30d, 90d, 180d and 360d (+14d) after surgery).

## **6.2 Trial Procedures**

The Trial Flow Chart - Section 6.0 summarizes the trial procedures to be performed at each visit. Individual trial procedures are described in detail below. It may be necessary to perform these procedures at unscheduled time points if deemed clinically necessary by the investigator.

Furthermore, additional evaluations/testing may be deemed necessary by the Principal Investigator and/or Merck for reasons related to subject safety. In some cases, such evaluation/testing may be potentially sensitive in nature (e.g., HIV, Hepatitis C, etc.), and thus local regulations may require that additional informed consent be obtained from the subject. In these cases, such evaluations/testing will be performed in accordance with those regulations.

### **6.2.1 Administrative Procedures**

#### **6.1.1.1 Informed Consent**

The Investigator must obtain documented consent from each potential subject prior to participating in a clinical trial.

Consent must be documented by the subject's dated signature or by the subject's legally acceptable representative's dated signature on a consent form along with the dated signature of the person conducting the consent discussion.

A copy of the signed and dated consent form should be given to the subject before participation in the trial.

The initial informed consent form, any subsequent revised written informed consent form and any written information provided to the subject must receive the IRB/ERC's approval/favorable opinion in advance of use. The subject or his/her legally acceptable representative should be informed in a timely manner if new information becomes available that may be relevant to the subject's willingness to continue participation in the trial. The communication of this information will be provided and documented via a revised consent form or addendum to the original consent form that captures the subject's dated signature or by the subject's legally acceptable representative's dated signature.

Specifics about a trial and the trial population will be added to the consent form template at the protocol level.

The informed consent will adhere to IRB/ERC requirements, applicable laws and regulations and Principal Investigator requirements.

#### ***6.2.1.1 Inclusion/Exclusion Criteria***

All inclusion and exclusion criteria will be reviewed by the investigator or qualified designee to

ensure that the subject qualifies for the trial.

#### *6.2.1.2 Medical History*

A medical history will be obtained by the investigator or qualified designee. Medical history will include all active conditions, and any condition diagnosed within the prior 10 years that are considered to be clinically significant by the Investigator. Details regarding the disease for which the subject has enrolled in this study will be recorded separately and not listed as medical history.

#### *6.2.1.3 Prior and Concomitant Medications Review*

##### *6.2.1.3.1 Prior Medications*

The investigator or qualified designee will review prior medication use, including any protocol-specified washout requirement, and record prior medication taken by the subject within 28 days before starting the trial. Treatment for the disease for which the subject has enrolled in this study will be recorded separately and not listed as a prior medication.

##### *6.2.1.3.2 Concomitant Medications*

The investigator or qualified designee will record medication, if any, taken by the subject during the trial. All medications related to reportable SAEs and ECIs should be recorded as defined in Section 7.2.

#### *6.2.1.4 Disease Details and Treatments*

##### *6.2.1.4.1 Disease Details*

The investigator or qualified designee will obtain prior and current details regarding disease status.

##### *6.2.1.4.2 Prior Treatment Details*

The investigator or qualified designee will review all prior cancer treatments including systemic treatments, radiation and surgeries.

##### *6.2.1.4.3 Subsequent Anti-Cancer Therapy Status*

The investigator or qualified designee will review all new anti-neoplastic therapy initiated after the last dose of trial treatment. If a subject initiates a new anti-cancer therapy within 30 days after the last dose of trial treatment, the 30-day Safety Follow-up visit must occur before the first dose of the new therapy. Once new anti-cancer therapy has been initiated the subject will move into survival follow-up.

#### *6.2.1.5 Assignment of Screening Number*

At the time of screening, the patient will be assigned a screening number.

#### *6.2.1.6 Assignment of Randomization Number*

At the time of randomization during dose expansion, the patient will be assigned a randomization number.

#### *6.2.1.7 Trial Compliance (Medication/Diet/Activity/Other)*

### 6.2.2 Clinical Procedures/Assessments

#### *6.2.2.1 Adverse Event (AE) Monitoring*

The investigator or qualified designee will assess each subject to evaluate for potential new or worsening AEs as specified in the Trial Flow Chart and more frequently if clinically indicated. Adverse experiences will be graded and recorded throughout the study and during the follow-up period according to NCI CTCAE Version 4.0 (see Section 11.2). Toxicities will be characterized in terms regarding seriousness, causality, toxicity grading, and action taken with regard to trial treatment.

Please refer to section 7.2 for detailed information regarding the assessment and recording of AEs.

#### *6.2.2.2 Full Physical Exam*

The investigator or qualified designee will perform a complete physical exam during the screening period. Clinically significant abnormal findings should be recorded as medical history. A full physical exam should be performed during screening.

#### *6.2.2.3 Directed Physical Exam*

For cycles that do not require a full physical exam per the Trial Flow Chart, the investigator or qualified designee will perform a directed physical exam as clinically indicated prior to trial treatment administration.

#### *6.2.2.4 Vital Signs*

The investigator or qualified designee will take vital signs at screening, prior to the administration of each dose of trial treatment and at treatment discontinuation as specified in the Trial Flow Chart (Section 6.0). Vital signs should include temperature, pulse, respiratory rate, weight and blood pressure. Height will be measured at screening only.

#### *6.2.2.5 Eastern Cooperative Oncology Group (ECOG) Performance Scale*

The investigator or qualified designee will assess ECOG status (see Section 11.1) at screening, prior to the administration of each dose of trial treatment and discontinuation of trial treatment as specified in the Trial Flow Chart.

### 6.2.2.6 Tumor Imaging and Assessment of Disease

All patients will undergo a full-body F-18 FDG PET/CT scan within 75 days prior to start of treatment or randomization (only during dose expansion). Patients with stage II and III disease should have a brain CT or MRI within 75 days prior to start of treatment.

Following the time of surgery, the investigator or qualified designee will assess disease with imaging studies according to the investigator's determination of the standard of care.

[figure not shown]
### 6.2.2.7 Tumor Tissue Collection and Correlative Studies Blood Sampling

Prior to treatment or randomization (only during dose expansion), tissue collections include fresh sampling (preferred) of the primary tumor (core or excisional biopsy) or archival tissue, due to safety and inaccessibility, and blood samples (please see Table 6, Trial Flow for details).

If the patient has clinically involved lymph nodes and investigation of the nodes is clinically warranted, every effort should be made to collect tissue via core needle biopsy from the involved lymph nodes. If bronchoscopy is performed, it is highly encouraged to collect lavage specimens as well, although this is not mandatory.

Research-donated blood will be collected prior to pembrolizumab infusion during cycle 1 and cycle 2; prior to surgical treatment, and at each post-treatment/safety follow-up visit (30d, 90d, 180d and 360d ( $\pm$ 14d) after surgery).

Overall Schema:

\* Cycle 2 of pembrolizumab should be given except as recommended per protocol, section 5.2.1.2.

\*\* SRT is delivered within 7 days +/- 3 days of second pembrolizumab cycle. If second cycle is not given due to discontinuation, SRT should not be given (patient should continue to surgery when deemed safe by treating surgeon).

^ Surgery will take place no later than 6 weeks following last dose of pembrolizumab, e.g. no later than week 7, or if two cycles of pembrolizumab were given, week 10.

# Adjuvant blood collection will take place at follow-up visits (30d, 90d, 180d and 360d ( $\pm$ 14d) after surgery).

### 6.2.3 Laboratory Procedures/Assessments

Details regarding specific laboratory procedures/assessments to be performed in this trial are provided below. Laboratory Safety Evaluations (Hematology, Chemistry and Urinalysis)

Laboratory tests for hematology, chemistry, urinalysis, and others are specified in Table 5.

**Table 5 Laboratory Tests**

Hematology	Chemistry	Urinalysis	Other
Hematocrit	Albumin	Blood	Serum $\beta$ -human chorionic gonadotropin†
Hemoglobin	Alkaline phosphatase	Glucose	( $\beta$ -hCG)†
Platelet count	Alanine aminotransferase (ALT)	Protein	PT (INR)
WBC (total and differential)	Aspartate aminotransferase (AST)	Specific gravity	aPTT
Red Blood Cell Count	Lactate dehydrogenase (LDH)	Microscopic exam (If abnormal)	Free thyroxine (T4)
Absolute Neutrophil Count	Carbon Dioxide ‡	results are noted	Thyroid stimulating hormone (TSH)
Absolute Lymphocyte Count	(CO 2 or bicarbonate)	Urine pregnancy test †	PK
	Uric Acid		Blood for correlative studies
	Calcium		
	Chloride		
	Glucose		
	Phosphorus		
	Potassium		
	Sodium		
	Magnesium		
	Total Bilirubin		
	Direct Bilirubin (If total bilirubin is elevated above the upper limit of normal)		
	Total protein		
	Blood Urea Nitrogen		
	Creatinine		

† Perform on women of childbearing potential only. If urine pregnancy results cannot be confirmed as negative, a serum pregnancy test will be required.

‡ If considered standard of care in your region.

After Cycle 1, pre-dose laboratory procedures can be conducted up to 72 hours prior to dosing. Results must be reviewed by the investigator or qualified designee and found to be acceptable prior to each dose of trial treatment.

#### 6.2.4 Blood Collections

All patients will have 4 (four) 10mL green top tubes of blood specimens collected prior to pembrolizumab infusion during cycle 1 and cycle 2, prior to surgical treatment, and at each post-treatment/safety follow-up visit (30d, 90d, 180d and 360d ( $\pm$ 14d) after surgery).

Sample collection, storage and shipment instructions for blood samples are provided in the Laboratory Manual.

#### 6.2.5 Other Procedures

Fresh sampling (preferred) of the primary tumor (core or excisional biopsy) is required, or archival tissue may be substituted for reasons due to safety and inaccessibility.

If the patient has clinically involved lymph nodes and investigation of the nodes is clinically warranted, every effort should be made to collect tissue via core needle biopsy from the involved lymph nodes.

##### *6.2.5.1 Pretreatment samples*

Core biopsies of primary tumor +/- involved lymph nodes will be performed by a qualified radiologist, pathologist, surgeon, or pulmonologist. One to four core biopsies will be performed (number determined by safe accessibility and size of lesion at the discretion of the physician performing the biopsy). Core biopsies are required, however if it is deemed technically infeasible, or if a core biopsy is deemed very high risk by the physician performing the biopsy, then fine-needle aspiration (FNA) may be acceptable in 1-2 extremely select cases based on pre-approval by the study Principal Investigators.

For intraparenchymal lung biopsies, an 18G core needle biopsy is preferred. If this is not considered to be safe by the physician performing the procedure, then an FNA with a higher gauge needle will be acceptable.

Biopsy sites other than intraparenchymal lung should use a 16 G if possible, but 18 G or FNA will be acceptable if the physician performing the biopsy feels that it is safer. One to three needle passes at minimum will be obtained, but if the physician determines it is safe, up to 6 passes may be obtained.

Sample collection, storage and shipment instructions for pre-treatment tissue samples are provided in the Laboratory Manual.

##### *6.2.5.2 Post-treatment samples:*

Patients will undergo surgical resection of their primary tumor and associated lymph nodes. Patients in cohort 1 will have received pembrolizumab alone prior to resection, whereas patients in cohort 2 will have received pembrolizumab and radiation to half of the primary tumor.

In all cases, post-treatment excisional samples should be first taken from the primary tumor tissue that was treated with pembrolizumab only (medially oriented half of tumor). The portion of tumor which received radiation is the lateral aspect of the tumor relative to the patient.

Therefore, mandated post-treatment tissue samples should always be removed from the medial aspect of the tumor.

If it is feasible and specimen collection will not interfere with the patient's clinical care, tissue samples should also be collected from the radiated portion of the tumor (lateral aspect). These tumor samples should be labeled so that their orientation (medial vs lateral) is clear.

Samples from clinically involved lymph nodes are requested if feasible and if collection will not interfere with the patient's clinical care. These samples should be labeled by the designated nodal station.

Sample collection, storage and shipment instructions for post-treatment tissue samples are provided in the Laboratory Manual.

#### *6.2.5.3 Lavage (fluid) specimens*

If bronchoscopy is performed, it is highly encouraged to collect lavage specimens as well, although this is not mandatory. If a patient has clinical indication for bronchoscopy, lavage fluid may be obtained. Any excess leftover fluid, up to 1000mL, should be submitted.

Sample collection, storage and shipment instructions for fluid samples are provided in the Laboratory Manual.

#### 6.2.6 Withdrawal/Discontinuation

When a subject discontinues/withdraws prior to trial completion, all applicable activities scheduled for the final trial visit should be performed at the time of discontinuation. Any adverse events which are present at the time of discontinuation/withdrawal should be followed in accordance with the safety requirements outlined in Section 7.2 - Assessing and Recording Adverse Events.

#### 6.2.7 Blinding/Unblinding

This trial is open label; therefore, the subject, the trial site personnel, the Principal Investigator and/or designee are not blinded to treatment.

#### 6.2.8 Visit Requirements

Visit requirements are outlined in Section 6.0 - Trial Flow Chart. Specific procedure-related details are provided above in Section 7.1 - Trial Procedures.

### 6.2.9 Screening

Screening period will be conducted days -28 to -1.

### 6.2.10 Treatment Period

Treatment will initiate with the first dose of pembrolizumab. A second dose of pembrolizumab will be delivered 3 weeks later, +/- 3 days.

If the patient is scheduled to receive SRT on the protocol, the day of radiation delivery will be no later than 7 days following the date anticipated for administration of the second cycle of pembrolizumab, +/- 3 days. If the second cycle is not given, then SRT should not be given.

Surgical resection, if the patient is medically and physically able to undergo the procedure, should be delivered no later than 6 weeks (42 days +/- 3 days) after the last dose of pembrolizumab.

### 6.2.11 Post-Treatment/Safety Follow-Up Visits

After the date of surgery, patients will return for clinical and laboratory assessments at 30 days (first follow-up visit), 90 days, 180 days, and 360 days (+/- 14 days) after the date of surgery. These assessments are required but imaging studies are to be ordered at the discretion of the investigator or a qualified designee.

All AEs that occur prior to the Safety Follow-Up Visit should be recorded. Subjects with an AE of Grade > 1 will be followed until the resolution of the AE to Grade 0-1 or until the beginning of a new anti-neoplastic therapy, whichever occurs first. SAEs that occur within 90 days of the end of treatment or before initiation of a new anti-cancer treatment should also be followed and recorded.

Every effort should be made to collect information regarding disease status until the start of new anti-neoplastic therapy, disease progression, death, end of the study. Information regarding post-study anti-neoplastic treatment will be collected if new treatment is initiated.

Correlative blood samples will be collected at each follow-up visit. Details are provided in Section 6.0 – Trial Flow Chart

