## 2.0 TRIAL DESIGN

### 2.1 Trial Design

This is a randomized single-institution, phase II, open-label clinical trial of neoadjuvant pembrolizumab with or without low-dose stereotactic radiation therapy (SRT) in stage I- IIIA non-small lung cancer (NSCLC) patients who are planned to undergo surgical resection of their lung cancer.

Two consecutive run-in cohorts will administer pembrolizumab or pembrolizumab with SRT of 12 Gy to the lateral aspect of the primary tumor. Patients will receive pembrolizumab for 2 cycles prior to surgery or SRT and surgery. Surgical resection of all involved areas of tumor will occur within 6 weeks of the last administration of pembrolizumab. It should be noted that in almost all cases, surgery is expected to occur very expeditiously, within a much shorter window and 6 weeks would represent only the greatest allowable amount of delay.

If during the run-in, only the pembrolizumab-alone cohort meets pre-specified safety parameters, subsequently enrolled patients will enter a larger expansion cohort, with treatment given according to that cohort only. If during the run-in both cohorts meet pre-specified safety parameters, subsequently enrolled patients will enter the expansion cohort and be randomized between preoperative pembrolizumab versus pembrolizumab with SRT of 12 Gy.

Patients will be followed every 12 weeks for 1 year for disease status and survival.

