# Adjuvant blood collection will take place at follow-up visits (30d, 90d, 180d and 360d ( $\pm$ 14d) after surgery).

Adjuvant therapy such as systemic therapy +/- radiation therapy following surgery will be administered according to the standard of care per judgment of the treating physician(s).

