#### 3.2 Secondary Objectives & Hypotheses

(1) **Objective:** To assess the safety of preoperative pembrolizumab +/- SRT when combined with surgery;

**Hypothesis:** In patients scheduled for NSCLC resection, pembrolizumab, or pembrolizumab + SRT, given in the preoperative window, will meet safety criteria described by the protocol;

(2) **Objective:** To record the toxicity of preoperative pembrolizumab +/- SRT when combined with surgery, according to CTCAE v. 4, including immune-related adverse events (AEs);

**Hypothesis:** In patients scheduled for NSCLC resection, pembrolizumab, or pembrolizumab + SRT, given in the preoperative window, will result in acceptable short-term and perioperative toxicity;

(3) **Objective:** To determine the 1-year overall survival rate resulting from preoperative pembrolizumab +/- SRT when combined with surgery;

**Hypothesis:** In patients scheduled for NSCLC resection, pembrolizumab + SRT given in the preoperative window will result in a higher 1-year survival rate than pembrolizumab alone;

(4) **Objective:** To determine the 1-year relapse free survival rate resulting from preoperative pembrolizumab +/- SRT when combined with surgery;

**Hypothesis:** In patients scheduled for NSCLC resection, pembrolizumab + SRT given in the preoperative window will result in a higher 1-year relapse free survival rate than pembrolizumab alone;

(5) **Objective:** To determine the 1-year rate of distant metastases resulting from preoperative pembrolizumab +/- SRT when combined with surgery;

**Hypothesis:** In patients scheduled for NSCLC resection, pembrolizumab + SRT given in the preoperative window will result in a lower 1-year distant metastasis rate than pembrolizumab alone;

(6) **Objective:** To assess quality of life associated with preoperative pembrolizumab +/- SRT when combined with surgery;

**Hypothesis:** In patients scheduled for NSCLC resection, pembrolizumab, or pembrolizumab + SRT, given in the preoperative window, will result in acceptable short-term and perioperative quality of life;

(7) **Objective:** To determine the rate of unresectability that results from a program of preoperative pembrolizumab +/- SRT to be followed by a planned surgery;

**Hypothesis:** In patients scheduled for NSCLC resection, either pembrolizumab or pembrolizumab + SRT given in the preoperative window will both result in <15% overall rate of unresectability following the preoperative program;

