### **4.3 Rationale**

#### **4.3.1 Rationale for the Trial and Selected Subject Population**

We hypothesize that neoadjuvant treatment with pembrolizumab and targeted stereotactic radiation therapy (SRT) will improve patients' immunogenic responses during and after surgical treatment of their non-small cell lung cancer. The timing of the interventions during the neoadjuvant phase will allow us to perform comprehensive analyses on tumor specimens before any treatment and after initial response to pembrolizumab alone or pembrolizumab with SRT.

In this study, patients are offered immunotherapy +/- SRT before surgery but are free to pursue chemotherapy +/- external beam radiation therapy after surgery. It is important to call attention to this deliberate aspect of the study design, which ends protocol-mandated treatment at the time of surgery, such that patients are allowed to pursue postoperative treatment appropriate to their surgical/pathologic stage. While chemotherapy is considered part of the perioperative standard of care for NSCLC patients undergoing resection, the only available randomized evidence showed no statistical difference in long-term disease-free survival, whether chemotherapy was administered preoperatively or postoperatively (Felip 2010). Thus, neoadjuvant chemotherapy given prior to surgery is not considered a standard of care, and in fact the extremely well established standard of care is to offer postoperative chemotherapy +/- radiotherapy depending on the pathologic outcome at surgery, as advocated by the guidelines issued by the European Society of Medical Oncologists on this subject (McElnay 2014). Likewise, there is no clear benefit to external beam radiotherapy whether given preoperatively or postoperatively. In addition, emerging recent evidence indicates that in several different tumor types, cisplatin may stimulate upregulation of PD-L1 and that this could be associated with subsequent cisplatin resistance (Zhang 2016, Mesnage 2016, Yan 2016). Therefore, the rationale for administration of immunotherapy prior to administration of cisplatin, with the possibility of inducing a durable immune response prior to surgery and expected postoperative therapy, may offer a more therapeutically effective strategy.

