### **5.8 Subject Withdrawal/Discontinuation Criteria**

Subjects may withdraw consent at any time for any reason or be dropped from the trial at the discretion of the investigator should any untoward effect occur. In addition, a subject may be withdrawn by the investigator or the Principal Investigator if enrollment into the trial is inappropriate, the trial plan is violated, or for administrative and/or other safety reasons. Specific details regarding discontinuation or withdrawal are provided in Section 7.1.4 – Other Procedures.

A subject must be discontinued from the trial for any of the following reasons:

- 5.9.5 The subject or legal representative (such as a parent or legal guardian) withdraws consent.
- 5.9.6 Confirmed radiographic disease progression
- 5.9.7 Intercurrent illness that prevents further administration of treatment per protocol
- 5.9.8 Investigator's decision to withdraw the subject
- 5.9.9 The subject has a confirmed positive serum pregnancy test
- 5.9.10 Noncompliance with trial treatment or procedure requirements
- 5.9.11 The subject is lost to follow-up
- 5.9.12 Administrative reasons

The End of Treatment and Follow-up visit procedures are listed in Section 6. After the end of treatment, each subject will be followed for 30 days for adverse event monitoring (serious adverse events will be collected for 90 days after the end of treatment). Subjects who discontinue for reasons other than progressive disease will have post-treatment follow-up for disease status until disease progression, initiating a non-study cancer treatment, withdrawing consent or becoming lost to follow-up. After documented disease progression each subject will be followed by telephone for overall survival until death, withdrawal of consent, or the end of the study, whichever occurs first.

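### The protocol conflicts with itself on whether relapse is recorded after adjuvant therapy starts, which puts 1-year relapse-free survival and distant metastasis at risk

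*Combined protocol and SAP*

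**What the plan says.** **Text that ends disease-status collection when new therapy starts**

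- Section 6.2.11: "Every effort should be made to collect information regarding disease status until the start of new anti-neoplastic therapy". The sentence goes on to list progression, death and the end of the study as further end points.
- Section 6.2.1.4.3: "Once new anti-cancer therapy has been initiated the subject will move into survival follow-up". The therapy in question is any begun after the last dose of trial treatment.
- Section 5.8 has a similar cut-off for a narrower group: "Subjects who discontinue for reasons other than progressive disease will have post-treatment follow-up for disease status until disease progression, initiating a non-study cancer treatment".

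**Text that continues it**

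- Section 2.1: "Patients will be followed every 12 weeks for 1 year for disease status and survival".
- Section 6.2.11 itself requires visits at 30, 90, 180 and 360 days after surgery.
- The flow chart in Section 6.1 lists "CT chest at 360d or as otherwise clinically indicated".

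**Text that makes adjuvant therapy an expected event**

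- The notes to the diagram in Section 2.2: "Adjuvant therapy such as systemic therapy +/- radiation therapy following surgery will be administered according to the standard of care".
- Section 4.3.1 describes the standard of care as being to "offer postoperative chemotherapy +/- radiotherapy depending on the pathologic outcome at surgery".

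**Endpoints that depend on the answer**

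Secondary objective 4 in Section 3.2 reads "To determine the 1-year relapse free survival rate resulting from preoperative pembrolizumab +/- SRT when combined with surgery". Objective 5 is the 1-year distant metastasis rate. Both carry a hypothesis comparing the two arms.

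**The concern.** A cut-off at new anti-cancer therapy suits a setting where new therapy signals progression. Here a patient can start adjuvant treatment within weeks of surgery with no relapse. A coordinator following Sections 6.2.11 and 6.2.1.4.3 would stop recording disease status at that point; one following Section 2.1 would continue to one year.

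The loss would not be random. Adjuvant therapy is tied to the pathologic outcome, so those whose follow-up is cut short are likely to differ in relapse risk from those followed to day 360. If pathologic outcome differs between arms, so could the loss.

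Section 4.4 calls these data exploratory, but it also makes them a starting point for deciding which of the two programs deserves further study.

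**Working it through.** **1. Is adjuvant therapy caught by the cut-off?** Section 6.2.1.4.3 counts therapy begun after the last trial dose, and Section 4.3.1 ends protocol treatment at surgery. Post-operative adjuvant therapy is therefore new, non-study therapy, and no section exempts it.

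**2. Does the analysis plan settle it?** No. The only analysis in Sections 7.1 and 7.2 is the exact binomial test of the CD3+ endpoint. There is no analysis, censoring or missing-data rule for RFS or distant metastasis.

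**3. How much follow-up is exposed?** The start of adjuvant therapy is not given. Assuming day 30, 60 or 90 after surgery, the part of the 360 days outside the collection duty is:

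- (360 − 30)/360 = 330/360 = 92%
- (360 − 60)/360 = 300/360 = 83%
- (360 − 90)/360 = 270/360 = 75%

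**4. What could this do to 1-year RFS?** The plan gives no figure to reproduce. N = 40 is from Section 7.2; every other input is assumed:

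- a share f on adjuvant therapy, starting at 2 months
- 1-year RFS of 0.70 with adjuvant therapy (Sa) and 0.90 without (Sn)
- constant hazards and no deaths without relapse
- nothing recorded after the cut-off

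At 2 months, Sa(2) = 0.70^(1/6) = 0.942 and Sn(2) = 0.90^(1/6) = 0.983. For f = 0.5:

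- True RFS = f·Sa(12) + (1−f)·Sn(12) = 0.35 + 0.45 = 0.800
- Unknown at 1 year = f·Sa(2) = 0.471, or 18.8 of 40 patients
- Bounds from recorded data alone = 0.450 to 0.450 + 0.471 = 0.921
- Kaplan-Meier censored at adjuvant start = [f·Sa(2) + (1−f)·Sn(2)]·Sn(12)/Sn(2) = 0.882
- Unknown patients excluded = 0.450/[0.5 + 0.5 × (1 − 0.942)] = 0.851
- No recorded relapse counted as relapse-free = 1 − [0.5 × 0.10 + 0.5 × (1 − 0.942)] = 0.921
- Relapses recorded = (1 − 0.921)/(1 − 0.800) = 39%, or 3.2 of 8.0

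| Share on adjuvant | Unknown of 40 | True RFS | Bounds | Kaplan-Meier | Excluded | No record = relapse-free | Relapses recorded |
|---|---|---|---|---|---|---|---|
| 30% | 11.3 | 84% | 63–91% | 89% | 88% | 91% | 55% |
| 50% | 18.8 | 80% | 45–92% | 88% | 85% | 92% | 39% |
| 70% | 26.4 | 76% | 27–93% | 87% | 79% | 93% | 29% |

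**5. Sensitivity at f = 0.5**

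- Start at month 1 or 3: Kaplan-Meier gives 89% or 87%, with 32% or 46% of relapses recorded.
- Equal 20% risk in both groups: true RFS is 80%. The three estimates are 80% (Kaplan-Meier, no bias), 77% and 88%, with 59% of relapses recorded.
- Visits go on recording disease status: no loss.

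**The case against.** The best counter-argument is that, read as a whole, the protocol intends disease status to be followed for the year.

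- Section 6.2.11 sets an effort standard, not a prohibition. It lists four end points without saying that the earliest governs, although its adverse-event sentence does say so.
- Survival follow-up is not defined as ending disease assessment. The one description of telephone contact for survival only, in Section 5.8, is triggered by progression.
- The flow chart puts post-study therapy status in the same follow-up column as examination and imaging, so patients on other therapy are expected at those visits.
- Blood draws continue through day 360 (Sections 2.2 and 6.2.2.7). Section 5.5.2 prohibits no therapy during follow-up. Section 6.2.2.6 has the investigator assess disease after surgery with no cut-off.

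These points stand as evidence of intent, and they are why the endpoints are at risk of being incomplete rather than certain to be lost. They do not override Section 6.2.1.4.3, which changes the patient's follow-up status outright. The continuing visits are described as clinical and laboratory assessments. The flow chart has rows for survival and later therapy but none for relapse. The 360-day CT is not a firm safeguard, because footnote h and Sections 6.2.2.6 and 6.2.11 leave follow-up imaging to the investigator.

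It is also fair that the illustration assumes the literal reading throughout, leaves out deaths (which would still be recorded and would count towards RFS), and does not model distant metastasis separately. Analysing without censoring at adjuvant start is one defensible choice among several, but the plan currently makes none.

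**Conclusion.** The concern holds. The current text gives conflicting instructions for a situation the protocol itself expects. The literal reading of Sections 6.2.11 and 6.2.1.4.3 would leave secondary objectives 4 and 5 informatively incomplete.

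The size depends on unknowns. It runs from no loss, if visits keep recording disease status, to roughly half the patients with unknown 1-year status and an RFS estimate 5 to 12 percentage points too high at 50% adjuvant use under the unequal-risk assumptions. With equal risk, the censored Kaplan-Meier estimate is unbiased but more than 40% of relapses still go unrecorded. That the conflict exists rests on the wording alone and needs none of these assumptions.

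The primary endpoint, overall survival and the unresectability rate are not touched. This should be fixed, but it does not threaten the trial's main conclusion.

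**What to change.** 1. In Sections 6.2.11 and 6.2.1.4.3, add: *Adjuvant therapy given in the absence of relapse does not end disease-status follow-up; relapse and distant metastasis status are recorded at the scheduled post-operative visits through day 360 for all patients.* Align Section 5.8 with this.
2. In Section 7.2, state that 1-year RFS and distant metastasis are analysed without censoring at the start of adjuvant therapy, and that the number of patients with unknown 1-year disease status is reported.

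The cost is a few sentences and completion of the case report form at visits already required. No visit is added and no treatment changes.

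Two related mismatches should be reconciled separately: the 360-day chest CT in the flow chart against the text leaving follow-up imaging to discretion, and the 12-weekly follow-up in Section 2.1 against the 30, 90, 180 and 360-day visits.
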